The patient will be asked if they are interested in releasing access to their medical records for up to 10 years after their participation in this study in order to allow study personnel to track the outcome and/or related procedures in the future. The patient can revoke their consent to this question at any time by contacting the Principal Investigator.

E. Risks, Benefits, Safety and Confidentiality:

The patient will be injected with an FDA approved radiopharmaceutical for the PET imaging session. The dose of the radiopharmaceutical will never exceed the recommended FDA dosing limits, and we anticipate that imaging will typically be done at substantially lower than maximum levels.

Risks:

The occurrence of any adverse events due to the conduct of the study is not foreseen. Risks associated with the investigational PET are considered very rare and are the same type of physical events that could occur in any normal PET scan. These would include pinching of skin, minor falls or bumps. Normal risks of a nuclear medicine scan from injection of a radiopharmaceutical include allergic reactions, swelling, infections, intravenous injuries, bruising, pain, and discomfort. Clinical guidelines for the PET will be followed according to OSUWMC hospital policy.

The CT scan performed will be used for attenuation correction of the PET imaging and for anatomic correlation of the PET images. The CT scan also involves radiation exposure. Long term exposure to radiation may slightly increase one's risk for cancer. The exposure risk is cumulative over a lifetime, and the total should be kept as low as possible. The exact long-term risks from radiation are not known. To give the participant an idea about how much radiation they will receive from PET/CT scan we will make a comparison with an every-day situation. Everyone is exposed to unavoidable radiation each year, known as background radiation. Some of this radiation comes from space and some from naturally-occurring radioactive forms of water and minerals. This research gives the participant's body at most the equivalent of about 5 extra years' worth of this natural radiation.

Benefits:

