It is hoped that the information from this study will provide preliminary, investigational information regarding the pathophysiological status of the disease/ailment/injury and may contribute to a more personalized diagnostic and/or therapeutic management in the future. All information obtained will be labeled as investigational in any communication to participating and/or referring physicians. The subject can request that a research report is provided to their healthcare provider of choice.

Safety Monitoring:

The well being of the subject will be monitored in a similar manner to all non-invasive imaging methodologies as participation does not present more than minimal risk. The Principal Investigators or Co-Investigators or Key Personnel are able to respond immediately to ensure the safety of the patients participating in the research study. The Principal and/or Co-Investigators or Key Personnel will be present at the time of all PET acquisitions to ensure this.

The duration of data acquisition in the PET system per patient is limited to no more than 2 hours total consisting of one or more acquisition series. There is no limit to the number of times an individual patient may participate in this study.

In the event of any medical emergency, accident or trauma while the subject is in the facility, our contingency plans for emergency situations are as they would be for any medical facility and clinical imaging facility. Our emergency protocol fully prepares us to provide access to emergency treatment for our patients, resuscitation, life support and medical care as needed.

Confidentiality of Records:

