All paper and electronic data/information will be de-identified prior to any review or analysis. All paper documents will be stored in a locked file cabinet with limited access in the Department of Radiology at The Ohio State University. All electronic data obtained through PACS or IHIS will be stored in a de-identified manner on password protected servers with limited access in the Department of Radiology at The Ohio State University. In the Informed Consent, we are asking subjects for release of medical records for up to ten years, as well as the use of de-identified data for other future studies. This data may be kept indefinitely by the Wright Center of Innovation for further assessment or reference. No individual identities will be used in any publications resulting from this study. If the subject has authorized the use of de-identified data for other research studies as comparative data, the de-identified data may be shared with collaborative investigators as well as research databases. The established processes to verify de-identified data will always be adhered to. Officials from examining bodies such as the U.S. Food and Drug Administration or NIH may inspect records pertaining to this study.

F. Internal Validity

Image data will be evaluated at a minimum following standard published procedures. This includes but is not limited to visual evaluation of lesions, normal tissue, sentinel nodes and imaging artifacts, semi-quantitative analysis, blinded reader analysis, and using various methods for image post-processing. This should ensure internal and external validity of the data and avoid study bias. Functional and molecular read outs will be developed according to established methodologies.

Managing and verifying the internal validity is an important task in this exploratory research program in order to develop the appropriate methodology to be validated in prospective clinical trials.

As there is an opportunity that the staff member administering the facility experience can potentially bias the subject, we will perform training sessions with the staff prior to them administering the facility experience. We will also perform from time to time an observational

assessment by a study member participating in the subject facility experience with the task to observe the team member administering the facility experience in order to ensure that no bias or systematic errors occur.

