This occurs when the subject-related variables, color of hair, skin color, etc., and the time-related variables, age, physical size, etc., interact. If a discrepancy between the two groups occurs between the testing, the discrepancy may be due to the age differences in the age categories.

Experimenter bias:

Experimenter bias occurs when the individuals who are conducting an experiment inadvertently affect the outcome by non-consciously behaving in different ways to members of control and experimental groups. It is possible to eliminate the possibility of experimenter bias through the use of double blind study designs, in which the experimenter is not aware of the condition to which a participant belongs.

G. Incidental Findings

Any incidental findings discovered will be correlated to any accessible standard of care imaging. If these incidental findings were not previously reported on standard of care imaging, the subject will be contacted according to the previous choice/request indicated on the informed consent form.

H. Data Analysis

The purpose of this trial is to perform exploratory assessment and as such will only use descriptive statistics. We do not intend to perform a statistical assessment beyond classifying the characteristics of pilot data and comparing observational trends either to the standard of care imaging data or other known reference data. For our purposes, imaging that presents lower imaging quality will not be pursued for further evaluation. Only images that suggest equivalent or improved image quality or diagnostic information compared to current standard of care imaging approaches would be evaluated for the potential use as data towards the design of a formal clinical trial and/or funding applications.

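### Does de-identifying all data before review make it impossible to report incidental findings, send requested reports or follow outcomes?

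*Protocol*

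**What the plan says.** The rule is in the Protocol, section III.E, Confidentiality of Records: "All paper and electronic data/information will be de-identified prior to any review or analysis". The same paragraph sets the storage rule, "All electronic data obtained through PACS or IHIS will be stored in a de-identified manner on password protected servers with limited access", and refers to existing procedures: "The established processes to verify de-identified data will always be adhered to". It does not describe a study code, a key, a key holder or a step for re-identification.

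Four other places need some link to the person:

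- Section III.G, Incidental Findings: "Any incidental findings discovered will be correlated to any accessible standard of care imaging". If the finding was not already reported there, "the subject will be contacted according to the previous choice/request indicated on the informed consent form".
- Section III.E, Benefits: "The subject can request that a research report is provided to their healthcare provider of choice".
- Section III.D, Release of Medical Records: optional access for up to 10 years, "in order to allow study personnel to track the outcome and/or related procedures in the future". The patient may withdraw this permission by contacting the principal investigator.
- Section III.E, Safety Monitoring: "There is no limit to the number of times an individual patient may participate in this study". Repeat scans therefore have to be recognised as coming from one person.

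**The concern.** The confidentiality sentence covers all data and any review, without exception. An incidental finding usually comes to light when an image is reviewed, and by then the rule has already removed the name. If no link survived, the finding could be neither compared with the person's clinical imaging nor passed on. Requested reports and later outcomes could not be attached to the right scan, and a repeat participant might be counted as several people.

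The first of these would be a safety matter. The others would weaken the comparison with standard of care imaging, which section III.H names as one of the two comparators. Each activity would fail for whichever of the 200 evaluable patients it concerned.

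**Working it through.** The Protocol gives no figure to reproduce. The question is whether its statements can all hold together, so they are set side by side.

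**1. Does the rule say the link is destroyed?** No. Section III.E does not say that de-identification is irreversible, that no key exists or that source records are deleted. The electronic data come from the hospital's image archive and record system and are then stored in de-identified form. The natural reading is a research copy, with the clinical originals left in place.

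**2. Do other sections presuppose a link?** Yes.
- Section III.A has patients authorise study personnel to consult their records, and asks separately about future use of their images in de-identified form. Identified access and de-identified use are thus two layers.
- Section III.D lets a patient revoke record access, which means nothing unless the team can tell whose access is revoked.
- Section III.E, Confidentiality of Records, repeats the ten-year release in the same paragraph as the rule, so its authors saw no conflict between the two.

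**3. What does each activity need?**

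| Activity | Obligation? | What it needs |
|---|---|---|
| Contact about an incidental finding | Yes, following the consent choice | Re-identification of one case |
| Report to a provider | Only on request | Re-identification of one case |
| Record follow-up | Optional, revocable | A key held by study personnel |
| Pairing with clinical scans, grouping repeat scans | Implied by the comparison and by repeat participation | A common study code, no name needed |

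Only the first row is a firm duty. The last row is fully compatible with de-identified images.

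**4. Can a size be put on it?** Not from the Protocol. It gives no rate of incidental findings. If 1% to 10% is assumed, 200 × 0.01 = 2 and 200 × 0.10 = 20 people would have a new finding. They would go uninformed only if no link existed and all had chosen to be contacted, and neither is stated.

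For repeat scans, assume three per patient and a within-patient correlation of 0.5 to 0.9; the Protocol gives neither. The design effect is 1 + (m − 1)ρ:
- ρ = 0.5: 1 + 2 × 0.5 = 2.0
- ρ = 0.9: 1 + 2 × 0.9 = 2.8

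Dividing 200 by these gives 100 and 71, but that treats 200 as a number of scans. The sample is 200 patients. At three scans each there are 600 scans, and 600 / 2.0 = 300 and 600 / 2.8 = 214, so the effective number does not fall below the number of patients. Treating the scans as independent would understate a standard error by √2.0 = 1.41 to √2.8 = 1.67. Section III.H, however, restricts the trial to descriptive statistics, so no planned standard error, interval or test is affected.

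**The case for a change.** The best case for a change is that one word does two jobs. Section III.E uses the same term for the team's working data and for data passed to collaborators and research databases. If it means unlinked, section III.G cannot be carried out from the study data. If it means coded, the reader is not told whether shared data can be traced back. Surviving clinical records do not settle this, because without a key a stripped image cannot be matched reliably to its source. The reference to established processes concerns verifying de-identification, not reversing it. A few sentences would resolve all of this at almost no cost, and the duty to contact a subject is a serious one.

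Much of this stands. The confidentiality sentence is unqualified, no key is described, and the tension with section III.G is real. What does not stand is the step from silence to impossibility. A protocol that offers revocable record access and promises contact according to the consent choice cannot sensibly be read as destroying the link. The consent form, where coding language would commonly appear, is not part of the text at hand, so its absence here shows nothing. Nor would the comparison with standard of care imaging be lost, since a code is enough for it. Section III.H also allows comparison with other known reference data, so later outcomes are not the only reference.

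**Conclusion.** No change to the plan follows. The wording in section III.E is loose and is not reconciled in so many words with section III.G. But this is a gap that any competent study team fills in the ordinary way: it codes images before reading, holds the key separately and uses it where the Protocol itself calls for contact, a report or follow-up. Writing that down would record what the team must do anyway and would alter no estimate, comparison or conclusion.

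The effect on the sample size and the descriptive analysis is nil. Any count of uninformed subjects or lost information depends on rates, scan numbers and correlations that the Protocol does not give.

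The conclusion rests on two assumptions: that de-identification here is reversible coding by authorised staff, as the record-access provisions imply, and that the clinical source records are kept. A statement elsewhere in the study documents that the link is destroyed before images are read would reopen the point, first of all for incidental findings.

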This prospective study will utilize investigational PET acquisitions on the newly available digital photon counting detector platform to develop and optimize PET acquisition and post-processing techniques as well as to generate preliminary and comparative data for potential confirmatory clinical trials. We will assess these innovations in regard but not limited to visual inspection of lesions, normal tissue, sentinel nodes and imaging artifacts, semi-quantitative and blinded reader analysis. The PET methodologies we plan to use as part of this study will allow us to obtain morphological, functional and molecular information in ways beyond any current standard of care imaging procedures.

We anticipate recruiting patients from 3 general populations. 1 – Patients enrolled in a clinical trial where innovative PET imaging may be beneficial to the trial, although not necessarily the individual patient. This would include patients enrolled in a clinical trial exploring a new treatment approach for whom imaging at other timepoints in treatment would not be covered by insurance and therefore not considered standard of care (SOC). 2 – Any patient with a concern for a medical condition / question not yet fully resolved by SOC practice for whom a treating physician believes that a research PET may have a potential to address the medical question and help for future patients with similar questions. For example, this could include a patient presenting with heel pain for whom standard x-ray shows no confirmation of injury, but the physician feels an innovative PET bone scan could help identify the cause of the pain. 3 – Any patient having a SOC PET scan who would be interested in receiving an investigational scan, either as part of or in addition to the SOC scan. This would include patients already scheduled for a SOC scan who would be willing to have an investigational PET acquisition immediately following the standard acquisition for example acquired with a shorter scan time. This would also include patients who have already had a SOC PET examination, but would be willing to have a second, investigational PET exam, with a significantly reduced radiotracer dose for example. Thus the radiation dose and exposure associated with the investigational imaging would be in addition to any standard of care imaging, although the two will be combined whenever appropriate.

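### Does the stray facility-experience wording in Section III.F leave image reading, and the Section III.H choice of images, without a bias control?

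*Protocol*

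**What the plan says.** Section III.F (Internal Validity) warns that "the staff member administering the facility experience can potentially bias the subject". It answers with two measures: "we will perform training sessions with the staff prior to them administering the facility experience", and an occasional observer whose task is "to observe the team member administering the facility experience in order to ensure that no bias or systematic errors occur". The paragraph on instrument change mentions self-reported perceptions of the facility, with retrospective pretesting as a remedy. It also names observers whose criteria shift without their noticing.

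The opening paragraph of the same section deals with image evaluation. It sets published procedures as the minimum and lists what they include: "sentinel nodes and imaging artifacts, semi-quantitative analysis, blinded reader analysis, and using various methods for image post-processing". It then says that this should secure validity and avoid bias. Section III.A (Research Design) gives a similar list: "normal tissue, sentinel nodes and imaging artifacts, semi-quantitative and blinded reader analysis".

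Section III.H (Data Analysis) limits the trial to descriptive statistics. Imaging of lower quality is dropped. Only images that look at least as good as current standard-of-care imaging, in quality or diagnostic information, are considered for designing a formal trial or for funding applications. The section does not say who makes that judgement or whether it is blinded.

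**The concern.** Two things look wrong. First, the only staff-directed controls in Section III.F that are concrete enough to carry out are tied to an activity the trial does not seem to contain. Participants give consent, receive a tracer, are scanned and may release their records. They are not taken through a facility experience and complete no questionnaire about the facility.

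Second, the judgement that matters most in a study of this kind, whether an investigational image is as good as the standard one, has no training, observation or calibration attached to it. Yet the protocol itself names observer drift as a threat. Section III.H then selects images on the outcome of that judgement without linking it to the blinded reading planned elsewhere. If an unblinded enthusiast made the selection, the pilot data carried into later trials and funding applications would look better than the technology deserves.

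**Working it through.** The protocol gives no error rate, margin, effect size or reader agreement from which a bias could be computed, so the check is textual.

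**1. Is the facility experience part of this trial?** The word facility occurs 8 times:

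| Place | Uses | Meaning |
|---|---|---|
| III.E, Safety Monitoring | 3 | the site, as in "any medical emergency, accident or trauma while the subject is in the facility" |
| III.F, opening part | 4 | facility experience |
| III.F, Instrument change | 1 | facility perceptions |

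That is 3 + 4 + 1 = 8, with none in Sections I, II, III.A to III.D, or III.H. The term is undefined and matches no procedure or measure. It could loosely mean the PET visit, since Section III.E uses the word for the place of imaging, but the fit is poor. Surrounding text on online surveys and on participants remembering their answers also points to wording borrowed from a different kind of study.

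**2. Were the two measures meant for readers?** No. The stated risk is that staff influence the subject ("the staff member administering the facility experience can potentially bias the subject"). Controls on staff-to-subject influence would not reach readers even if the facility experience were a defined procedure. Of the 2 measures, 2 concern the facility experience and 0 name readers. That count shows what the measures are for. It does not show that reading is uncontrolled, so the misplaced wording is not the cause of any gap in reading.

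**3. What controls image reading?** Blinded reader analysis appears twice, once in Section III.A and once in Section III.F. In III.F it belongs to the minimum set for evaluating image data, and the text gives avoidance of bias as the purpose. Drift has no measure of its own beyond the general promise in III.F to keep assessing sources of bias. The device quality control mentioned beside it concerns the scanner. Blinding does bear on primed observers, who are named in the same sentence as drift.

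**4. Does Section III.H depart from this?** It mentions blinded reading 0 times, but it neither gives the judgement to unblinded staff nor exempts it from Section III.F. Deciding whether an image matches the standard is itself an evaluation of image data, so the III.F minimum can fairly be read as covering it. What is missing is a cross-reference.

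**5. Would a rewrite gain anything?** Deleting the facility text alters nothing that is done to participants or concluded from them. Training and observing readers, masking acquisition type, dose and scan time, and randomising reading order would be new duties. They would not come free with the existing de-identification step ("All paper and electronic data/information will be de-identified prior to any review or analysis"), which the protocol describes as protecting identity. Paired reading is assured only where a standard scan exists by definition, which is 1 of the 3 populations in Section III.A ("Any patient having a SOC PET scan who would be interested in receiving an investigational scan"). Using other reference data for the remaining 2 would change the Section III.H test, which is framed against standard-of-care imaging.

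**The case for a change.** The strongest case for a change is that this is an error in what the protocol states, and not a detail left to another document. A promised control has no object, and the threat it ought to address is named and then left with only a general promise. Blinding hides which scan is which, but it does not by itself stop a reader's criteria from moving over the course of the study. Section III.F also lists several evaluation methods without saying which one decides. A sponsor could therefore hold blinded reads and still choose images on an open visual impression without breaching the letter of Section III.H. The remedy would be a few sentences.

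Much of this is factually right. The term is undefined, drift has no dedicated measure, and the link from the reading to the selection is left to inference. It does not show that a stated rule gives a wrong answer. An open-label selection would satisfy Section III.H read alone, but it would sit badly with the minimum in Section III.F, and a sponsor following the whole plan would use the blinded reads. Which read decides, how images are masked and in what order they are shown are matters commonly settled in a statistical analysis plan or reader manual. Neither is at hand, so their absence from the protocol is not evidence that they are missing.

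**Conclusion.** No change to the plan is needed. The facility wording is a clerical slip: five phrases in Section III.F (four uses of facility experience, one of facility perceptions) that correspond to nothing the trial does. Removing them would tidy the text without altering conduct or conclusions. The silence in Section III.H is a gap that analysts can fill sensibly from the blinded reading already planned in Sections III.A and III.F. A cross-reference would be a courtesy to the reader, and no result depends on it.

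The stakes are low because the trial is exploratory, tests no hypothesis and reports only descriptive statistics. The worst consequence is a flattering choice of pilot images, whose size cannot be computed from the document.

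The conclusion rests on three assumptions: that the facility experience is carried-over text, which is inferred from its absence elsewhere; that the III.F minimum applies to the Section III.H judgement; and that operational reading detail sits in a document not shown. If the sponsor in fact let unblinded staff select the images, the concern would be a real one.

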Protocol Title: Feasibility Assessment of Next-generation PET Technology and Procedures

Protocol Date: September 12, 2017

Research Project Number: RP0506

Principal Investigator: [name], PhD
Professor of Radiology and Novartis Chair of Imaging Research
Vice Chair of Research, Department of Radiology
[name]
[name]

[contact]

Office: [contact]
[contact]

I. Objectives

The purpose of this study is to assess the feasibility of investigational Positron Emission Tomography (PET) imaging using the new generation digital detector PET technology for new procedures beyond the current standard of care:

1. To enable innovative PET imaging in association with a clinical trial to add potential future biomarker readouts for disease characterization and therapy management.
2. To generate preliminary and comparative imaging data for potential confirmatory clinical trials using innovative imaging timepoints, acquisition, dose, and timing approaches, and/or post-processing procedures.
3. To explore digital PET imaging for new indications where PET is not currently considered a standard of care diagnostic procedure in order to be able to design future clinical trials.

II. Background and Rationale

PET imaging is increasingly being used as a diagnostic modality in cancer detection and staging, neuro-molecular assessment, cardiovascular-molecular imaging, physiological/musculoskeletal imaging, and response assessment. Additionally, PET imaging is utilized in the detection and assessment of inflammatory processes. Constant advances in detector technology, image acquisition, and post-processing approaches could lead to the increased utility of PET in many currently unmet clinical scenarios.

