We have already performed an intra-individual comparison trial demonstrating advanced capabilities of digital PET technology in regard to lesion detection, lesion characterization, quantification, duration of scan time, and reduction of radiation dose. The digital PET is now fully FDA approved and in this trial we need to generate preliminary data in order to design prospective clinical trials that allow the validation of a hypothesis. We have demonstrated the safety of the system [now FDA approved] and the overall efficacy in relation to current clinical care practice standards, however, the technology enables the change of those standards for which we need to demonstrate the clinical feasibility that we have either shown in pre-clinical PET imaging or via simulations.

This research focuses on evaluating the new capabilities of PET imaging which may be improved or enabled by a new generation of fully digital PET systems. In order to change clinical practice, we need to first generate data on the potential capabilities of this major technology improvement. We will be performing and evaluating investigational PET/CT imaging beyond the current standard of care practice. Prior studies by our team have already performed comparisons between the new and current PET imaging, however the digital PET studies were constrained by being performed as a comparison to standard of care. In this clinical trial, we can conduct research studies at innovative time points or using innovative procedures currently not covered by insurance, such as repeat imaging prior to treatment or midway through treatment for replanning purposes or to find better quantitative readouts to improve diagnosis and disease management. We intend to conduct PET imaging also for indications not typically covered by insurance, such as cardiac, neuro-related, or orthopedic/sportsmedicine indications. We may also perform imaging with FDA approved radiotracers beyond their normal use (off-label) to explore the synergistic capabilities of the new generation of PET imaging.

III. Procedures

A. Research Design

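### Section III.H does not fix whether images or approaches are screened out; read per image, it forwards results selected on their own outcome, and its two criteria do not fit together (minor)

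*Protocol*

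**What the plan says.** Section III.H (Data Analysis) limits the trial to descriptive statistics. It commits, without restriction, to "comparing observational trends either to the standard of care imaging data or other known reference data". Two screening sentences follow.

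- First sentence: "imaging that presents lower imaging quality will not be pursued for further evaluation". The criterion is image quality alone, and no comparator is named.
- Second sentence: "Only images that suggest equivalent or improved image quality or diagnostic information compared to current standard of care imaging approaches would be evaluated", and the purpose is "for the potential use as data towards the design of a formal clinical trial and/or funding applications". The criterion is quality or diagnostic information, and the comparator is standard of care.

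Neither sentence says whether the decision is taken for a single image, a patient or an acquisition approach.

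Data for later trials are a main product of the study. Objective 2 in Section I reads "To generate preliminary and comparative imaging data for potential confirmatory clinical trials", and Section II repeats the aim: "in this trial we need to generate preliminary data in order to design prospective clinical trials". For the third recruitment population, Section III.A gives two examples that sit alongside a standard scan: patients "willing to have an investigational PET acquisition immediately following the standard acquisition for example acquired with a shorter scan time", and patients who "would be willing to have a second, investigational PET exam, with a significantly reduced radiotracer dose for example".

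**The concern.** If the second sentence is applied image by image, an image becomes candidate data because it compared well with standard of care. That comparison is the quantity a later designer would want to estimate. A mean difference or success proportion taken from the kept images would then be too favourable wherever a fair share of images came out worse. With a shorter scan or a lower tracer dose, the worse images plausibly mark where quality begins to fail. That is an inference, but it makes them the images a designer would most need.

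The two sentences also use different criteria. An image of lower quality that keeps or improves the diagnostic information is stopped by the first sentence and not stopped by the second. Staff applying Section III.H cannot tell what to do with it.

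Section III.F lists threats to validity, including selection bias and differential attrition. It describes these as differences between subjects, self-selection and dropout. None of the listed threats describes choosing images by their result, so that section does not cure the problem.

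**Working it through.** The protocol gives no SD, margin, failure rate or effect size, so there is no figure of its own to reproduce. The check has two parts.

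**1. The two criteria side by side**

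| Quality vs standard | Diagnostic information vs standard | First sentence | Second sentence |
|---|---|---|---|
| lower | lower | stopped | stopped |
| lower | equal or better | stopped | not stopped |
| equal or better | lower | passes | not stopped |
| equal or better | equal or better | passes | not stopped |

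The outcomes differ in one row of four. Every image that passes the first sentence already satisfies the second. If both are applied, the diagnostic-information alternative therefore never changes a decision.

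**2. Size of the selection effect (illustration only)**

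All inputs are assumptions:
- The difference from standard of care is Normal with mean δ and SD 1, for quality and for diagnostic information, with the same δ for both.
- The correlation r between the two runs from 0 to 0.8.
- The cut c is 0, or −0.5 if equivalent is taken to tolerate 0.5 SD.
- The model applies only where a standard-of-care PET exists.

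Write a = c − δ, φ and Φ for the standard normal density and distribution function, and P = Φ₂(a, a; r) for the probability that both differences fall below the cut.

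*Per image, quality or diagnostic information.* Share kept = 1 − P. Mean quality difference among kept images = δ + (1 + r) φ(a) Φ(a√((1 − r)/(1 + r))) / (1 − P).

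- δ = 0, c = 0, r = 0: P = 0.25; mean = 0.399 × 0.5 / 0.75 = +0.27, keeping 75%.
- δ = 0, c = 0, r = 0.8: P = 0.398; mean = 1.8 × 0.399 × 0.5 / 0.602 = +0.60, keeping 60%.
- δ = 0, c = −0.5: +0.12 (keeping 90%) at r = 0, to +0.35 (keeping 78%) at r = 0.8.
- δ = −0.5: −0.03 to +0.40 with c = 0, and −0.23 to +0.10 with c = −0.5.
- δ = +2: between +2.00 and about +2.02 under either cut, so almost no bias.

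*Per image, quality alone.* Share kept = 1 − Φ(a); mean = δ + φ(a)/(1 − Φ(a)). At δ = 0 and c = 0 this is 0.399/0.5 = +0.80, keeping 50%. At c = −0.5 it is +0.51, keeping 69%.

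*Per approach, on the mean quality of 10 images.* The same formula with SD 1/√10 = 0.316. At δ = 0 and c = 0: 0.316 × 0.399/0.5 = +0.25. At c = −0.5: 0.316 × 0.114/0.943 = +0.04. At δ = −0.5 and c = 0, an approach passes only 6% of the time, but those that pass show +0.14, which is 0.64 above the truth.

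*Images on which the two sentences give different outcomes.* Share = Φ(a) − P. For δ from −0.5 to 0 and either cut, this runs from 9% to 25%.

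**The case against.** The strongest reply is that Section III.H describes a go/no-go on techniques. The second sentence compares with standard-of-care imaging approaches, and Objective 2 speaks of acquisition, dose and timing approaches. Dropping a technique that looks poor is what a feasibility study is for. This stands as a legitimate reading, and under it the effect at a true difference of 0 is small. It does not settle the matter, because the subject of the second sentence is images, and the mismatch of criteria is the same at either level.

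A reader might infer that the two sentences contradict each other outright. They do not. The second states a necessary condition, so an image of lower quality with good diagnostic information is not admitted by it, merely not excluded. Both sentences can be obeyed at once. What remains is a clause with no effect and an unclear instruction.

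A reader might also infer that worse images are left out of this trial's results, or that Objective 2 is defeated. The text does not support that. The comparison of observational trends is unrestricted and can itself supply comparative data. Nothing says that worse images are deleted or hidden. Nor does the protocol say that an effect size will be computed from the kept subset: the images are only evaluated for potential use.

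Finally, detailed tabulation may properly sit in a statistical analysis plan, which is not at hand. That is fair, but the point concerns a rule the protocol itself states, not an absent table.

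**Conclusion.** The point holds as a minor one. Section III.H must fix its unit of selection and use one criterion. As written, it permits selection of images on their own result for data meant to inform later trials or funding.

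The bias arises only if a later design or application takes a summary from the kept images alone. This trial tests no hypothesis, and no error rate or sample size of its own is affected.

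The size rests wholly on the assumed normal model. At a true difference of 0, the quality-or-diagnostic rule applied per image gives about +0.1 to +0.6 SD; a decision per approach on the quality of 10 images gives +0.04 to +0.25 SD. The effect is close to nil where few images are worse. The per-approach reading is not harmless in general: a truly worse approach that passes by chance still looks too good, although it seldom passes.

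**What to change.** Replace the last two sentences of Section III.H with text to this effect:

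*The decision to pursue an acquisition approach is made per approach, on all investigational images acquired with it. The criterion is [image quality alone / image quality or diagnostic information], equivalent to or better than standard of care or the reference used. Any summary or comparative result used for trial design or a funding application is computed from all images of that approach and is given with the numbers worse, equivalent and better. Single images may be shown if labelled as illustrations.*

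The sponsor chooses one of the bracketed criteria and keeps its freedom to drop an approach.

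The cost is one paragraph and some extra scoring of images already acquired, with no added patients or scans. Forwarded results will look less favourable. Choosing approaches on few images still leaves a residual selection effect, which the counts help a reader to judge but do not remove.
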